2. Is this a multi-center study where the Penn IRB will be asked to serve as the IRB of Record for other external study sites?

No

Other Sites

No other sites

Protocol

Abstract

Cardiovascular disease is the leading cause of death in the US. While prevention approaches have improved longevity of patients, risk factors and adverse health behaviors (e.g., physical inactivity, smoking) are highly prevalent. The logistics and practicalities of meeting the goal of ideal CV health have not been clearly elucidated. Practice guidelines recommend using the Framingham risk score (FRS) or other risk prediction tools to classify patients risk of CV disease. These models however are imprecise and there is increasing focus on identifying markers that provide better measures of risk. As digital platforms are increasingly used to document lifestyle and health behaviors, data from digital sources may provide a window into manifestations of novel risk factors and potentially a better characterization of existing risk factors.

Objectives

Overall objectives

This study has three main objectives. (1) Identify and characterize topics and features derived from digital data (e.g., social media, online search, mobile media) which are associated with CHD and related risk factors and develop phenotypes of how patients use and engage with social media and then determine the association of these phenotypes with health status, social media perceptions, and patient activation. (2) Quantify and validate the incremental benefit of adding variables from patients' digital data to conventionally-derived predictive models of CHD (e.g. Framingham risk score/American College of Cardiology ASCVD Risk Estimator Plus) using a retrospective cohort of patients with and without heart disease. (3) In a cohort of patients with and without heart disease, develop and evaluate models that use digital media data to predict health care utilization (e.g. cost). (4) Evaluate the impact of dynamic health events (e.g. COVID-19) on modifiable CV health behaviors (smoking, diet, activity) using population level-digital media data (e.g. Facebook, Twitter)

Primary outcome variable(s)

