The primary outcome variable for the first objective will be topics and features (derived using the Latent Dirichlet Allocation [LDA] method for clustering language data) as well as a model-based approach of latent class analysis (LCA). We hypothesize: H1: There will be a difference in themes and topics posted by patients with heart disease and for patients without heart disease and use and engagement

phenotypes reflecting quantity, quality, and interaction of posts will be associated with health status, social media perceptions, and patient activation. The second objective outcome variable will be any CHD event. We hypothesize: H2: Adding digital data variables to conventionally-derived predictive models will improve the AUC for forecasting/predicting a CHD related event in a patient. The third objective outcome measure will be health care utilization measured by cost. We hypothesize: H3: Unique digital data variables identified for patients with heart disease and without heart disease will better predict future health care utilization costs for the health system. The fourth objective outcome measure will be the impact of dynamic health events on CV health behaviors. We have the following three hypotheses: H4,1: Digital media data will provide valid measures of health behaviors when compared with traditional sources. H4,2: Variations in digital data about modifiable CV health behaviors will correlate with dynamic health events. H4,3: Modifiable CV health behaviors (smoking, poor diet, and reduced physical activity) will increase more in response to dynamic health events in low income and minority communities.

Secondary outcome variable(s)

Given the correlational nature of this research the distinction between primary and secondary outcome variables is not particularly apparent.

Background

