
opportunity is in the ability of digital platforms to not only provide markers of health but also serve as platforms that can be used for direct intervention. For example, Facebook now allows users to flag posts within their network that they think may suggest suicidal ideation. Facebook then anonymously provides resources for potential individuals at risk. To expand the scale of this type of intervention for mental health and other disorders would require calibrated algorithms with high sensitivity and specificity. The potential in CV health is in tracking, codifying, and better understanding the hard to measure lifestyle choices and exposures related to diet, exercise, smoking and others which can significantly contribute to development and progression of heart disease. At present measuring many of these behaviors is dependent on self-report and recall. Yet, posts or images from digital media could better inform a patient-provider discussion about how to change for example actual dietary choices and consumption. Standing in the way of this potential promise are a host of questions that require further scientific study about the social acceptability and logistic feasibility of collecting ongoing streams of data from individuals, about the analytic approaches essential for identifying associations between those data and more conventional representations of individual health, and about the application of those associations for research and for individual and population health. Further needed is a better understanding of the accuracy of the data, motivations for posting, representativeness (are posts actually by the person assigned), missing data (what behaviors are not captured intentionally or unintentionally) and others. The proposed project represents an entirely new area of study in looking at multiple digital media outputs and their association with CV risk and health care utilization. Understanding the collection, interpretation, and use of these new data streams represents a pioneering exploration of potentially great and enduring value. Ideal cardiovascular health (CVH) is based on 7 modifiable CV factors and behaviors (smoking, BMI, diet, physical activity, smoking status).⁷⁴ Low risk with respect to these collective measures is associated with reduced CV and stroke incidence and mortality.⁸⁷ Only 5% of US Adults have 6 metrics in the ideal range.⁷³ Modifiable CV behaviors are tracked through different validated nationally representative surveys (e.g. NHANES) but the output from these surveys often lag significantly in their availability for researchers and providers. Therefore, there are significant limitations in being able to develop public health interventions to address population level changes in health behaviors in near real time. Less is known about how modifiable health behaviors change in response to dynamic public health events. On March 11, the World Health Organization declared novel coronavirus (COVID-19) a global pandemic and identified that it was associated with an infodemic of information online.⁸⁸ As millions of Americans were required to shelter in place, health behaviors were notably altered and social media use exponentially increased.⁸⁹ Quarantine and sheltering in place have been associated with increased stress, anxiety, exacerbation of mental health conditions, and alterations in diet, weight, and physical activity.⁹⁰ In the era of COVID-19, disparities in care and outcomes have already been described.^{91, 92} The impact of COVID-19 is predicted to be longstanding due to alterations in the economy, education, and other areas of society which impact health. We will use advanced computational models for identifying and codifying health behaviors by region over time and in real time. This can inform strategies that health systems and public health departments can deploy for addressing the immediate and long-term CV health of the patients and communities they serve. Ideal CV health is ideal but making lifestyle and behavioral changes is hard.^{99, 100} Digital interventions can be used to enhance self-management of diabetes and modifiable behaviors like smoking cessation.¹⁰¹⁻¹⁰³ Of increased focused, engagement phenotypes that help explain how individuals use and engage with technology can be used for tailoring behavioral interventions and sustained behavioral change.⁷⁶ While marketers routinely use this information for increasing interest in products, there is limited data on how patient phenotypes (developed from consenting patients) could be used for personalized health interventions using social media data and social media platforms.

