
Study duration

It will take approximately 15-60 minutes during one session, but could take up to a week or more depending on completion of all enrollment steps for a participant to complete the study. For remote enrollment, it could take up to a week or more for participants to complete the eligibility survey, baseline survey, and share their digital data. If there are technical difficulties with our data collection application, we will ask participants who are opting to share Instagram if we can record their Instagram username for manual data extraction. Additionally, we will reach back out to them at a later time to share through our data collection application if there were any technical difficulties. All recruitment and follow up emails will be A/B tested, also known as split testing, the process of comparing two identical versions of an email. Potential variations include the order of information, email headers, and signatures. We aim to recruit 1000 participants over 4 years. Additionally, participants who agree to participate in the optional survey and interview will have to wait until a date and time is determined for the focus group to occur. Follow-up is necessary in this case.

Resources necessary for human research protection

Describe research staff and justify that the staff are adequate in number and qualifications to conduct the research. Describe how you will ensure that all staff assisting with the research are adequately

informed about the protocol and their research related duties. Please allow adequate time for the researchers to conduct and complete the research. Please confirm that there are adequate facilities for the research.

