
some patients and not others. As the dependent variable will be cost, we will be attentive to informative censoring and right skewness, potentially using generalized linear models under a gamma distribution and log link. To account for informative censoring we will use inverse probability of censoring weighting. We will also explore the application of our new nested g-computation approach that allows for informative censoring and time- varying covariates to obtain future cost predictions. Additionally, we will generate summary statistics to describe the cohort and survey responses. We will use the model-based approach of latent class analysis (LCA)- to classify individuals into previously unmeasured subgroups. Variables to include in the LCA will include: demographics, years of platform use, posting: volume, quality, retransmission, and engagement. We will use the Bayesian information criterion to assess goodness of model fit, entropy to assess variations between classes, and the parametric bootstrapped likelihood ratio test to assess if a model with  $k$  classes has better performance than  $k-1$  classes. We will then use a regression model to compare with measures of health status, social media perceptions, and readiness/activation for each latent class. Models will be adjusted for demographics.

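### The SAP lists demographics among the variables that form the engagement classes and then adjusts for demographics: classes can become partly demographic, and the adjusted comparison can lose power

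*SAP*

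**What the plan says.** The latent class analysis is described at the end of the SAP's Final Analysis Plan, after the Objective 3 text, although it serves Objective 1. Its inputs are given in one undivided list: "Variables to include in the LCA will include: demographics, years of platform use, posting: volume, quality, retransmission, and engagement". The number of classes is judged by the Bayesian information criterion (BIC), entropy and a bootstrapped likelihood ratio test. The outcome step follows: "We will then use a regression model to compare with measures of health status, social media perceptions, and readiness/activation for each latent class". The last sentence is "Models will be adjusted for demographics". The Protocol's Analysis Plan has the same text.

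The Protocol describes the construct three times, each time without demographics:

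- Overall objectives, Objective 1: "develop phenotypes of how patients use and engage with social media".
- Primary outcome variable(s), H1: "phenotypes reflecting quantity, quality, and interaction of posts will be associated with health status, social media perceptions, and patient activation".
- Background: "engagement phenotypes that help explain how individuals use and engage with technology".

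Neither document names the demographic variables, gives them a separate role in the latent class model, or plans a class model without them.

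**The concern.** H1 asks whether patterns of use and engagement relate to health status, perceptions and activation. A latent class model groups people by whichever indicators hang together. If several demographic items correlate with one another, the model can spend classes on describing that correlation. Two things follow. The reported phenotypes become a mixture of engagement and demographic groups, which is harder to read as H1 intends. And because the outcome regression also conditions on demographics, part of the variation between classes is removed again, while the engagement contrast is spread over more class terms. A real engagement association can then be missed more often. Adjusting for demographics is not the fault; using the same variables to define the classes is.

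**Working it through.** **1. No figure to reproduce.** The documents give no power calculation for this analysis. The Protocol (Study duration) says "We aim to recruit 1000 participants over 4 years", which is a recruitment target for the whole study. Alpha, effect size, number of classes, the demographic items and the number completing the Objective 1 survey are not stated. Everything below rests on assumed values, with SD 1 and a two-sided 5% level.

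**2. Cost of overlap between class and covariates.** Take two equal classes, a difference of d SD and total n, with demographics explaining a share R² of class membership. Then power ≈ Φ(d·√[n(1−R²)/4] − 1.96). With n = 1000 and d = 0.2:

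- R² = 0: 0.2 × √250 = 3.162, and Φ(1.202) = 0.885.
- R² = 0.5: 0.2 × √125 = 2.236, and Φ(0.276) = 0.609.

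**3. Main simulation.** Two engagement classes, five binary engagement items with probabilities 0.75/0.25, and an effect of 0.30 SD. Five binary demographic items come from a demographic grouping independent of engagement. With item probabilities p and 1−p in two equal demographic groups, the correlation between items is r = (2p−1)²:

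- p = 0.60 gives 0.04
- p = 0.675 gives 0.12
- p = 0.70 gives 0.16
- p = 0.75 gives 0.25

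The class model was fitted by EM, with BIC choosing from 1 to 4 classes. The outcome was tested by a joint F-test on assigned class, adjusted for the demographic items. Both versions used the same simulated data. There were 200 replicates per setting, except 500 at n = 500, r = 0.25 and 300 at n = 1000, r = 0.25.

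| n | r | Power, engagement items only | Power, demographics added | Mean classes, demographics added |
|---|---|---|---|---|
| 300 | 0.04 | 53% | 52% | – |
| 300 | 0.12 | 54% | 50% | – |
| 300 | 0.25 | 51% | 33% | – |
| 500 | 0.04 | 72% | 72% | 2.0 |
| 500 | 0.12 | 74% | 68% | 2.3 |
| 500 | 0.16 | 74% | 60% | 2.9 |
| 500 | 0.25 | 76% | 53% | 3.4 |
| 1000 | 0.04 | 97% | 97% | – |
| 1000 | 0.12 | 97% | 91% | – |
| 1000 | 0.16 | 96% | 86% | – |
| 1000 | 0.25 | 96% | 87% | – |

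At r = 0.25 the paired difference is 22.8 points (SE 2.0) for n = 500 and 9.0 points (SE 1.7) for n = 1000. Repeat runs of the n = 500, r = 0.25 setting gave 79% vs 57%, 73.5% vs 50.5% and 76% vs 54%.

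**4. False positives.** With no engagement effect and demographics affecting the outcome (n = 500, r = 0.25, 400 replicates), rejection rates were 4.0% without and 4.5% with demographics in the class model.

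**5. Fewer demographic items.**

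- Two items, r = 0.25: 73% vs 74% at n = 500, and 97% vs 95% at n = 1000.
- Three items, n = 500: 80.5% vs 79.5% at r = 0.12, and 80% vs 66.5% at r = 0.25.

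**6. Demographic and engagement groups related** (five items, r = 0.25).

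- n = 500: 73% vs 50% at a correlation of 0.3 between the groupings, and 61% vs 47% at 0.6.
- n = 1000, groupings agreeing for 70% of people: 93.5% vs 81%.

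**7. A second design.** n = 1000, effect 0.25 SD, engagement items at 0.7/0.3, four demographic items, BIC choosing from 2 to 4 classes, 80 replicates (error 5 to 6 points).

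- Weak demographic clustering: 76% vs 71%, within simulation error.
- Moderate and strong clustering, unrelated to engagement: 72.5% vs 50% and 70% vs 47.5%.
- Moderate and strong clustering, related to engagement: 76.2% vs 48.7% and 65% vs 43.8%.

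Under moderate or strong clustering the loss is 21 to 28 points. The mean number of classes rises from 2.0 to between 3.0 and 3.9. The share of class membership explained by demographics rises from 0.004–0.06 to 0.31–0.40.

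**The case against.** The strongest reply is that the list does not call its members indicators. Latent class models can take covariates of class membership, and demographics may be meant that way. That reading is possible, but the text gives demographics no different role from posting volume or engagement, so the sentence needs amending on either reading.

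Second, mixed demographic and engagement segments could be useful for tailoring interventions, which the Background mentions. That is a legitimate aim, but it is not what H1 states.

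Third, the loss can be nil. The Protocol's survey description labels income and education as socioeconomic status, and the SAP treats SES separately under Objective 2. If demographics here means only two or three weakly related items, the runs show little or no loss. This stands, and it is why the size is conditional; without a list of variables, the harmful case cannot be excluded.

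Fourth, the simulations chose classes by BIC alone and used a joint F-test on assigned class. The SAP also uses entropy and a bootstrapped likelihood ratio test, and says only that a regression model will be fitted. This also stands, so the figures show direction and plausible size, not a forecast.

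**Conclusion.** The concern holds. The textual conflict is plain: demographics are in the class-forming list and in the adjustment set, while the phenotypes are defined by use and engagement alone. The loss of interpretability does not depend on any power figure. The loss of power does: it needs several demographic items that correlate with one another.

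In the 0.30 SD design with unrelated groupings, the loss ran from none to about 23 points at n = 500 and from none to about 10 points at n = 1000, where power is already close to its ceiling. The related-groupings run at n = 1000 lost 12.5 points, and the 0.25 SD design lost more. These ranges belong to the settings run and do not bound the loss. No inflation of false positives was seen. This is an inexpensive improvement that should be made, not a threat to the validity of the test.

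**What to change.** In the SAP's Final Analysis Plan and the Protocol's Analysis Plan, remove demographics from the list of class-forming variables, so that classes rest only on years of platform use and on posting volume, quality, retransmission and engagement. Name the demographic variables and keep them as covariates in the outcome regressions. If they are also wanted in the class model, state that they enter as covariates of class membership and not as indicators. Report the demographic make-up of each class in a table. If the team prefers to keep mixed segments, it should say so in H1 and pre-specify a sensitivity class model without demographics.

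The cost is one sentence in each document, with no new data. The only thing given up is that demographic profiles describe the classes instead of helping to define them.

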
features with survey data. For example, NHANES survey questions (e.g. Do you now smoke cigarettes?) would be compared with images of cigarette smoking. For Objective 2: We will compare prediction models with and without digital variables. Probability weighted Cox proportional hazard analysis with robust variance estimates will be used to assess the association between each variable from digital media and CHD in univariable and multivariable models. We will use graphical and analytical methods to test the proportional hazards assumption for each analysis. To evaluate the predictive strength of digital data, we will build four predictive machine learning models using a stepwise sequence to select the most parsimonious model using combinations of risk factors. (1. Framingham predictors / American College of Cardiology ASCVD Risk Estimator Plus alone, 2. Framingham predictors / American College of Cardiology ASCVD Risk Estimator Plus + SES, 3. Framingham predictors / American College of Cardiology ASCVD Risk Estimator Plus + digital topics/features, 4. Framingham predictors / American College of Cardiology ASCVD Risk Estimator Plus + digital topics/features+ SES) For Objective 3: We will use Super Learner, the ensemble machine learning approach which allows for the specification of multiple plausible candidate prediction models. Each of the candidate models is applied to a training set and outcomes are predicted using the validation set. A loss function is calculated within each validation set and then averaged across validation sets, which provides the estimated cross-validated risk score for each method. Calibration will be assessed using a calibration plot comparing the predicted probabilities (obtained using fixed regression coefficients of the prediction models) with the observed probabilities. The Super Learner algorithm finds the optimal weighted combination across all of the specified methods. Van der Laan et al. proved the asymptotic efficiency of the Super Learner algorithm and demonstrated that the optimal combination performs at least as well as the best estimators from the candidate models. We will implement Super Learner in R (The R Foundation for Statistical Computing). In this approach generalized estimating equation (GEE) and generalized linear mixed effects models will be explored to account for repeated measures per patient over time. One of the challenges of cost analyses is censoring, since cost may be incomplete and available for some patients and not others. As the dependent variable will be cost, we will be attentive to informative censoring and right skewness, potentially using generalized linear models under a gamma distribution and log link. To account for informative censoring we will use inverse probability of censoring weighting. We will also explore the application of our new nested g-computation approach that allows for informative censoring and time-varying covariates to obtain future cost predictions. Additionally, we will generate summary statistics to describe the cohort and survey responses. We will use the model-based approach of latent class analysis (LCA)- to classify individuals into previously unmeasured subgroups. Variables to include in the LCA will include: demographics, years of platform use, posting: volume, quality, retransmission, and engagement. We will use the Bayesian information criterion to assess goodness of model fit, entropy to assess variations between classes, and the parametric bootstrapped likelihood ratio test to assess if a model with k classes has better performance than k-1 classes. We will then use a regression model to compare with measures of health status, social media perceptions, and readiness/activation for each latent class. Models will be adjusted for demographics.

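### The criteria for the number of engagement phenotypes compare only class models, so correlated indicators from one continuous scale would usually be reported as at least two subgroups

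*SAP*

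**What the plan says.** The closing part of the SAP's Final Analysis Plan introduces latent class analysis "to classify individuals into previously unmeasured subgroups". Its inputs are given as: "Variables to include in the LCA will include: demographics, years of platform use, posting: volume, quality, retransmission, and engagement". On choosing the number of classes it says: "We will use the Bayesian information criterion to assess goodness of model fit, entropy to assess variations between classes", followed by "the parametric bootstrapped likelihood ratio test to assess if a model with" k classes improves on one with k-1. The protocol's Analysis Plan carries the same text ("the parametric bootstrapped likelihood ratio test to assess if a model with k classes has better performance than k-1 classes"). Health status, social media perceptions and activation are then compared across classes by regression, adjusted for demographics.

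Neither document names a model in which the indicators correlate without any classes, or a check for dependence within classes. Neither gives a significance level, a maximum number of classes or a rule for criteria that disagree. Indicator coding and the number of people entering the class analysis are also unstated. The protocol's Study duration section says "We aim to recruit 1000 participants over 4 years". However, its inclusion criteria accept a Google account or a step tracker alone, so fewer than 1000 may have posts to analyse.

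**The concern.** The protocol's Primary outcome variable(s) section makes latent class analysis part of the Objective 1 outcome. H1 is partly a claim about these phenotypes, and the Background section presents engagement phenotypes as a basis for tailoring interventions. Whether distinct groups of users exist therefore matters to what Objective 1 can conclude.

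The parametric bootstrap draws its reference data from the fitted k-1 class model. In the standard form of that model, indicators are independent within each class. For k = 2 the reference data therefore have no association between any indicators. Years of use, posting volume, quality, retransmission and engagement describe one activity and can be expected to correlate. Any such correlation is evidence against that null, whether it comes from separate groups or from a smooth scale of low to high activity. The test then answers whether the indicators are related, not whether there are subgroups.

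The other criteria do not close the gap. BIC is compared only among class models, and entropy describes how well separated the classes are once they are assumed. No listed criterion can return a continuum without subgroups, so the reported phenotypes could be bands of a single scale.

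**Working it through.** The documents give no error rate, class count or power for this analysis, so there is no stated figure to reproduce. The check is a simulation in which no classes exist.

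**Inputs.** From the documents: the four posting measures, years of use, the test of k against k-1, BIC, and the recruitment target of 1000. Assumed: independence within class; five indicators cut at tertiles; one normal engagement factor with equal loadings λ; level 5%; N of 200, 500 and 1000. The correlation between two indicators before the cut is λ², so loadings 0.3, 0.5 and 0.7 give 0.09, 0.25 and 0.49.

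**Test.** LR = 2(log-likelihood with k classes minus log-likelihood with k-1), referred to 99 data sets drawn from the fitted k-1 class model, with 100 replicates per setting.

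**BIC.** One class has 5 × 2 = 10 parameters, two have 2 × 10 + 1 = 21, and three have 3 × 10 + 2 = 32. BIC accepts one more class when LR exceeds 11 ln N, which is 58.3, 68.4 and 76.0 for N = 200, 500 and 1000.

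| Correlation | N | 1 v 2 test rejects | Mean LR, 1 v 2 | 11 ln N | BIC prefers 2 to 1 | 2 v 3 test rejects |
|---|---|---|---|---|---|---|
| 0 (control) | 200 | 3% | 18.9 | 58.3 | 0% | - |
| 0 (control) | 500 | 5% | 18.4 | 68.4 | 0% | - |
| 0 (control) | 1000 | 6% | 17.4 | 76.0 | 0% | - |
| 0.09 | 200 | 32% | 23.8 | 58.3 | 0% | 4% |
| 0.09 | 500 | 81% | 37.4 | 68.4 | 2% | 1% |
| 0.09 | 1000 | 100% | 56.1 | 76.0 | 6% | 5% |
| 0.25 | 200 | 99% | 69.0 | 58.3 | 73% | 4% |
| 0.25 | 500 | 100% | 151.0 | 68.4 | 100% | 28% |
| 0.25 | 1000 | 100% | 294.0 | 76.0 | 100% | not available |
| 0.49 | 200 | 100% | 198.7 | 58.3 | 100% | 76% |
| 0.49 | 500 | 100% | 478.3 | 68.4 | 100% | 99% |

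No result is available for correlation 0.49 at N = 1000. The control rows show that the test keeps its level when its own null holds, so the excess comes from the null model.

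**Supporting runs.**
- With unequal loadings (0.3, 0.8, 0.5, 0.7, 0.7), 1 v 2 rejected in 100% at n = 300 and n = 1000. The 2 v 3 test rejected in 60% and 100%.
- With continuous indicators in a Gaussian profile model at N = 200, 1 v 2 rejected in 2% at loading 0 and 55% at loading 0.3, so tertile coding is not the cause.
- With the bootstrap null drawn from a one-factor model, false two-class findings were 2%, 5% and 7% at N = 200 and 2%, 2% and 10% at N = 1000, for loadings 0.3, 0.5 and 0.7. The Monte Carlo standard error is √(0.05 × 0.95/60), about 3 points.

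**Information lost by banding (illustration).** With the unequal loadings and n = 300, assigned class kept 48% of the factor's variance and a simple score kept 71%. For an assumed factor-outcome correlation of 0.15, R² is 0.0225 × 0.48 = 0.0108 by class and 0.0225 × 0.71 = 0.0160 by score. Power at n = 300 is then 44% and 60%.

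**Does BIC separate a factor from classes?** With no classes it chose the one-factor model in 25/25 data sets (n = 300) and 20/20 (n = 1000). One set of runs with three genuine classes gave a class model in 20/20 and 15/15. With genuine classes at ordered levels it often failed:
- three classes 1.25 SD apart: factor chosen in 20/20 at both sizes;
- two classes 1.0 SD apart: factor chosen in 20/20 at both sizes;
- two classes 1.5 SD apart: factor chosen in 5/20 (50/50 split) and 9/20 (70/30 split) at n = 300, and in 0/20 at n = 1000.

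**The case against.** The plan aims to classify people, and H1 asks only whether phenotypes are associated with health status, perceptions and activation. The protocol calls the work correlational, sets no error rate on the number of classes, and does not say that the classes are natural kinds. Bands of low, medium and high engagement could still be useful for tailoring. This stands in part: nothing here shows an inflated error rate in the regressions on class, and an association could be real. What the plan cannot support is reading the classes as distinct subgroups.

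The simulated model is also not the planned one. It leaves out demographics and assumes a single dimension, and H1 names quantity, quality and interaction, which need not form one scale. This limits the exact percentages. It does not rescue the null, because adding demographics means that they too must be unrelated to each other and to posting.

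Some stronger readings are tempting but not supported:
- That the bootstrapped test alone sets the number of classes. The SAP lists three criteria without ranking them.
- That subgroups appear nearly every time. At correlation 0.09 the test rejects in 32% at N = 200, and BIC prefers two classes in only 0-6% at any N, so the outcome depends on which criterion is followed.
- That the number of bands grows steadily with sample size. A third class was frequent only with strong correlation.
- That retransmission and engagement enter as totals tied to volume. No scaling is given.

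**Conclusion.** The concern holds in bounded form. The stated criteria cannot distinguish subgroups from a single engagement scale. If the indicators correlate through such a scale, the test of one against two classes rejects in 99-100% at correlation 0.25 or above for the sample sizes with results (N from 200). At correlation 0.09 it rejects in 32%, 81% and 100% at N = 200, 500 and 1000. BIC among class models gives no protection once the correlation reaches 0.25: it prefers two classes in 73% at N = 200 and 100% at N = 500 and 1000.

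This rests on independence within class, which is the usual default but is not stated in the documents, and on assumed correlations, coding, level and sample size. The power figures are illustrative only.

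A reader might infer that no subgroups exist, or that the phenotype associations are invalid. Neither follows: the documents contain no data on the question, and the defect concerns what the class criteria can show.

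**What to change.** In the latent class text of both the SAP's Final Analysis Plan and the protocol's Analysis Plan:

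1. Fit a one-factor (continuous latent trait) model to the use and posting indicators, leaving demographics out of that model, and report its BIC beside the models with 1 to k classes. Fit the class models to the same indicators for this comparison, so that the BIC values are comparable.
2. Run the planned regressions on health status, perceptions and activation with the continuous engagement score as well as with class.
3. State that the bootstrapped test and BIC among class models do not by themselves show that distinct subgroups exist. Claim distinct subgroups only if a class model fits better than the factor model. Otherwise report the classes as descriptive bands, and say that the data do not distinguish classes from a continuum.
4. Do not use the BIC comparison to drop the class analysis or to conclude that there are no subgroups. It often prefers the factor model when genuine classes are ordered or the sample is small.

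The cost is SAP and protocol wording, one extra model and one extra set of regressions on data already held. The subgroup wording may have to be softened.
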